## REVISION HISTORY

Version	Date	Description	Author
1.0	06/10/2020	Original	FC and CD
1.1	07/22/2020	Content revision. Clarified procedures of participant and data intake.	FC and MM
1.2	08/05/2020	Content revision. Added intervention program for digital PT group.	FC and MM
1.3	08/19/2020	Content revision. Added intervention program for conventional PT group.	CD and FC
1.4	08/24/2020	Content revision. Clarification of method to collect session by session information, Added study contacts.	FC
1.5	08/26/2020	Updated patient stipend section. Updated intervention program for conventional PT.	CD and FC

## SH-RCT-LBP-US-01 Clinical Investigation Protocol

### 1. BACKGROUND

Low back pain (LBP) has for long been the world's leading cause of years leaved with disability, and, considering that the overall life expectancy is rising, this pandemic only tends to get worse. Nearly everyone is affected by LBP at some moment in life (70-80% of lifetime prevalence). As a consequence, LBP is also presented as a leading cause of work absenteeism worldwide. Thus, although the estimate costs of LBP may be difficult to compare between different countries, its overwhelming socio-economic impact in modern society is evident.

In the absence of an effective treatment, LBP can become chronic, causing a huge impact in patients' daily life, and ultimately promoting a high consumption of healthcare resources. In the US alone, health expenditures for adults with spinal problems were estimated at \$6000 per person, representing a total cost of \$102 billion each year.

The dim picture described above highlights the urgent need for effective interventions that minimize disability, improve quality of life and decrease productivity losses.

Current guidelines on CLBP management recommend patient education, exercise, physical therapy (PT), and behavioural therapy as the mainstay treatments for this condition.

Despite some discrepancy in the type of exercise program (e.g. aquatic exercises, stretching, back schools, McKenzie exercise approach, yoga, tai-chi) and mode of delivery (e.g., individually designed programs, supervised home exercise, and group exercise), exercise therapy is recommended nearly transversally, with most studies concluding that exercise intervention programs should include a combination of muscular strength, flexibility and aerobic fitness exercises. Moreover, home exercises with a regular therapist follow-up has proven highly effective.

This is not, however, how LBP is currently managed. Appropriate patient education and structured behavioural training are rarely provided, and opioid prescription is also a common practice, despite known opioid-related morbidity and mortality rates. Because the prevalence of CLBP is

## SH-RCT-LBP-US-01 Clinical Investigation Protocol

continuously rising, and opioid misuse is an issue of great concern globally, identifying effective nonopioid alternatives for CLBP is of paramount importance.

Further compounding this problem, from the patients who are directed to PT, almost half give up after just 4 sessions, and only 30% complete their programs.

In this context, new ways of delivering care are much needed. Crucially, these need to: a) address the three pillars of care to achieve good and sustained clinical outcomes; b) overcome barriers to access; c) ensure patients are engaged throughout the programs; d) be scalable and cost-efficient.

Thus, SWORD Health has developed a digital care program to address these needs.

### **2. SWORD HEALTH DIGITAL CARE PROGRAMS**

SWORD Health's Digital Care programs address the three pillars of musculoskeletal care: therapeutic exercise, patient education and cognitive behavioural therapy (CBT).

The exercise component is delivered through a digital feedback system - SWORD Phoenix®- which is an FDA-listed class I medical device. This device uses motion tracking technology to digitize motion and provide real-time biofeedback on performance during exercise execution (see more below). This allows individuals to perform independent exercise sessions at home without the need for constant face-to-face therapist supervision, while still being remotely monitored (asynchronously) through a cloud-based Portal.

The safety and effectiveness of digital exercise programs performed with this device, in a home-based scenario, have already been demonstrated for recovery after total knee and hip arthroplasty. In these studies, where digital programs based on this device were compared with conventional PT, the clinical outcomes were superior in the digital group. These results were explained by (a) the positive impact of a kinematic biofeedback tool on patient performance, especially regarding error correction and stimulation of a greater range of motion; (b) patient empowerment regarding their rehabilitation process; (c) high patient engagement through the use

## SH-RCT-LBP-US-01 Clinical Investigation Protocol

of gamification strategies; (d) the positive effect of remote monitoring on patient effort and (e) the availability of objective data for clinical review, enabling data-driven decisions.

The educational component is delivered through a smartphone app. Each individual is presented with educational content on their condition, in the form of small articles curated by SWORD's clinical team, focusing on subjects ranging from anatomy and physiology, pain, exercise and fear avoidant behaviours.

A dedicated third-generation Cognitive Behavioural Therapy (CBT) program, which takes the form of a self-paced program consisting of written and pre-recorded audio materials, is also made available to the individual, through a secure email platform.

### 3. SYSTEM TECHNICAL SPECIFICATIONS

**SWORD Phoenix®** is a proprietary, 510(K) exempt, class I medical device, with CE mark, which is composed of the following three interconnected components:

- **Motion trackers**, placed on body segments using Velcro® straps. Each motion tracker is placed in a specific position. To assist in the correct placement of the motion trackers, both the trackers and the matching straps are color-coded. The motion trackers' setup varies according to each therapy.
- **Mobile App**, that comes pre-installed on a tablet, that guides the patient in each exercise session. Before each exercise, the patient is presented with a real-life video and audio explanation of that exercise. The execution interface is subsequently shown. This screen features: a) a progress bar; b) a repetition counter; c) a star counter and d) a timer displaying time left in the exercise. A correct repetition is defined as a movement starting at the baseline and reaching or surpassing the specified target, without violating movement or posture constraints. In case the patient violates a constraint, a message is prompted showing which movement error was performed, so that the patient can correct the movement in the following attempts. For each correct repetition, the patient earns from 1 to 5 stars, depending on the range

## SH-RCT-LBP-US-01 Clinical Investigation Protocol

of motion of that specific movement in comparison to normative values for that movement. At the end of each session, the patient is presented with a summary of the number of completed repetitions and stars, as well as with badges rewarding him for the progresses achieved in each exercise.

- **Web-based Portal** that allows the clinical team to generate new patient profiles and create exercise sessions for each patient. To prescribe a session, the clinician needs to select the exercises, number of sets and number of repetitions. When a patient performs a session, the results are uploaded to the platform and available for review. Based on this information, the clinical team can edit the parameters of each exercise according to patient performance and progress.

## 4. SECURITY AND DATA STORAGE

### 4.1 DATABASE

The networks where SWORD Health's infrastructure is hosted are maintained by Google and are included in Google Cloud Platform's SOC2 and HITRUST certifications. Security-related configurations are registered and verified periodically.

Collected data is stored in databases that are only accessible to SWORD's Application Programming Interface (API), and Personal Health Information (PHI) is individually encrypted inside this database. Separate databases are used for development, QA, and production environments.

### 4.2 WEB PORTAL

Data is secured in transit to SWORD's Application Programming Interface (APIs) due to enforced application of TLS 1.2 or above. Additionally, a web application firewall protects our servers from Cross-site Scripting (XSS) and SQL Injection attacks.

Access to SWORD's Web Portal is provided only to individuals who have a valid work contract with SWORD Health and have a role within the company that allows them to use the platform (i.e. PTs and IT support).

## SH-RCT-LBP-US-01 Clinical Investigation Protocol

Access control mechanisms ensure that only authorized users have access to PHI and different functions are mapped to different roles within the platform (i.e. IT support personnel only have access to de-identified data).

### 4.3 WEBSITE

SWORD's Onboarding Website does not have a login function as it works only as a registry platform and user accounts are created in SWORD's Web Portal. Data is secured in transit to SWORD's Application Programming Interface (APIs) due to enforced application of TLS 1.2 or above. Additionally, a web application firewall protects our servers from Cross-site Scripting (XSS) and SQL Injection attacks.

### 4.4 MOBILE APP

For an individual to access the mobile app in the medical device, their profile must be created in SWORD's Web Portal. Upon profile creation, the individual is attributed a unique QR card that is shipped together with the medical device kit. Upon the first usage, the individual is required to set a personal pin code (two-factor authentication is employed, as the user must scan their QR code and input a confirmation code sent by text message. This is required for the first login, with subsequent logins being done by presenting the pin and the QR card. Each session expires within 24 hours, requiring the individual to present these again if >24 hours have passed since the last usage.

Transport Layer Security (TLS) protocols are applied on every connection to ensure secure data transmission between the mobile app and the Database. Additionally, data stored in the device is also encrypted.

## 5. STUDY OBJECTIVE

To assess the clinical outcomes of a digital program for chronic low back pain versus conventional PT.

## 6. STUDY HYPOTHESIS

The digital program will be associated with at least the same outcomes as conventional PT.

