### 8. STUDY OUTCOMES

#### 8.1 Primary Outcome

Impact on functional disability measured through the Oswestry Disability Index score (patient reported outcome measure) between baseline and 8 weeks.

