## **9. SAMPLE SIZE ESTIMATION**

Sample size estimation calculations were performed taking into consideration the primary outcome measure – The Oswestry Disability Index (ODI). In the absence of similar studies, the calculations were made considering the study by Stankovic et al. (2012). This was a large study (n=160 patients), which compared two different rehabilitation protocols for CLBP and which used the same primary outcome as the present study. In this study, the standard deviation of the ODI at baseline was 17.83 points. A Minimal Clinically Important Change (MCIC) of 10 points was considered, based on the study by Ostelo et al. Considering a power of 80% and a two-sided 0.05 significance level, 102 individuals will be necessary to detect a 10-point difference between the two groups.

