### 15. ASSESSMENTS AND SPECIFIC DATA COLLECTION

Patients will be assessed at baseline, 4 and 8 weeks. All questionnaires will be collected through the EDC system. These will need to be filled within 5 consecutive days. To promote compliance with this schedule, whenever the deadline is approaching, automatic email reminders will be sent to participants. Participants will be excluded from the study for protocol breach in case they don't fill in the assessment forms.

Regarding the **baseline assessment**, participants will be asked to complete the survey before the start of the program. This assessment will include all the information pertaining to the primary and secondary outcomes, as well as the following information:

- a) date of birth
- b) gender
- c) height & weight
- d) body mass index
- e) formal education (years of schooling)
- f) job type
- g) baseline physical activity level
- h) previous back surgery (> 3 months ago)
- i) risk factors: working status, smoking status

For the **4- and 8-week assessment**, participants will be required to complete the questionnaire within a 5-day window beginning at the start of week 4 and 8. These assessments will include all the information pertaining to the primary and secondary outcomes. Physical activity will be measured only at baseline and 8 week assessment.

For participants on the digital group, engagement and usage metrics of the educational and CBT components will also be collected automatically.

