## 16. STATISTICAL ANALYSIS PLAN

To assess differences in clinical and demographic variables of the patients allocated to the two study groups, independent samples t test or Mann–Whitney U test will be used for quantitative variables. For categorical variables, Chi-square test or Fisher's exact test will be used.

Outcome analysis will be performed using both an intention to treat analysis and a per-protocol analysis.

The overall impact of the intervention on the primary and secondary outcomes will be assessed considering both the results at the 12-week assessment as well as change from baseline.

Differences between interventions will be evaluated using independent samples t test or Mann–Whitney U test. For non-normally distributed variables, the magnitude of the difference in the medians will be assessed using Hodges-Lehman estimator. Additionally, a repeated measures ANOVA will also be performed, with group as an independent factor and time as a within-subjects factor. When necessary, logarithmic transformation will be performed to obtain normally distributed variables. In all analysis, a significant level of 0.05 will be considered.

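### The hypothesis is non-inferiority in form, but the plan gives no margin or rule for concluding it when the two arms are similar

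*Combined protocol and SAP*

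**What the plan says.** Section 6 contains the only hypothesis: "The digital program will be associated with at least the same outcomes as conventional PT". Section 5 (objective) and section 7 (design) name no framework: superiority, non-inferiority and equivalence are all unmentioned.

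The other sections are written for a difference:

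- **Section 9.** "Considering a power of 80% and a two-sided 0.05 significance level", the conclusion is that "102 individuals will be necessary to detect a 10-point difference between the two groups". The SD comes from an earlier trial in which "the standard deviation of the ODI at baseline was 17.83 points". The 10 points is introduced as a minimal clinically important change and used as the difference to detect. It is never called a margin.
- **Section 16.** "Differences between interventions will be evaluated using independent samples t test" or its rank-based alternative, with a repeated measures ANOVA in addition, all at 0.05. For non-normal variables, "the magnitude of the difference in the medians will be assessed using Hodges-Lehman estimator". No interval or bound accompanies that estimate.

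The quantity to be compared is also not settled. Section 8.1 defines the primary outcome as "Impact on functional disability measured through the Oswestry Disability Index score (patient reported outcome measure) between baseline and 8 weeks". Section 15 says "Patients will be assessed at baseline, 4 and 8 weeks". Section 16, however, refers to results at 12 weeks as well as to change from baseline. It also plans both intention-to-treat and per-protocol analyses without saying which one decides.

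**The concern.** A hypothesis that counts equality as success needs three things fixed in advance: how much worse the new programme may be (the margin), the interval to set against that margin, and the quantity and analysis set to which the rule applies. The plan has none of these.

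A significant result favouring digital would support section 6. The gap is the case where the arms come out similar, which section 6 explicitly includes. The expected result there is a non-significant test, and a non-significant test does not show that digital is no worse. A margin chosen after the data are seen would not be a pre-specified test. A trial run exactly as written therefore cannot answer its own hypothesis in that case.

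**Working it through.** **Inputs from the plan.** SD 17.83 (a baseline value), difference 10, power 80%, two-sided 0.05, total 102 (all section 9).

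**Assumptions.** 1:1 allocation, so 51 per arm (section 13 gives two groups and blocks of 6 but no ratio). No dropout unless stated. The same SD at 8 weeks as at baseline. True difference 0 and one-sided 0.025 for non-inferiority. The margins, correlations, alternative SDs and reduced numbers below are not in the documents.

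**1. Reproduce 102.** A two-sample t test (noncentral t) for 10/17.83 needs 50.88 per arm, so 51 per arm and 102 in total. Power at 51 per arm is 80.1%; at 50 per arm it is 79.3%. The stated figure is thus a two-sided test of difference with no allowance for dropout.

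The same formula applies to a margin of 10 with true difference 0, so the match does not show that a margin was intended.

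**2. What the planned test yields if the arms are equal.** Any 0.05 test is then non-significant with probability 1 − 0.05 = 95%. The two-sided test significantly favours digital 2.5% of the time.

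**3. Precision with 102 patients, unadjusted 8-week score.**

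- SE = 17.83 × √(2/51) = 3.53.
- 95% half-width = t(100; 0.975) × SE = 1.984 × 3.53 = 7.0 points.

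**4. Non-inferiority power, unadjusted score.** Power = P(T > 1.984), where T is noncentral t with 100 df and noncentrality margin/SE.

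| Margin (assumed) | Power |
|---|---|
| 10 | 80% |
| 9 | 71% |
| 8 | 61% |
| 5 | 29% |

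The smallest margin with 80% power is 10.0. If the SD were 15 or 20, power at margin 10 would be 92% or 71%. With 45, 40 or 35 analysed per arm, it would be 75%, 70% or 64%.

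**5. Dependence on the quantity chosen.** For correlation r between baseline and 8 weeks:

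- SD of change = 17.83 × √(2(1 − r)) = 21.10, 17.83, 13.81 at r = 0.3, 0.5, 0.7.
- SD of the baseline-adjusted score = 17.83 × √(1 − r²) = 17.01, 15.44, 12.73.

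| Quantity | r | Half-width | Power, margin 10 | Power, margin 8 | Smallest margin for 80% | Total N for 80% at margin 8 |
|---|---|---|---|---|---|---|
| 8-week score | – | 7.0 | 80% | 61% | 10.0 | 158 |
| Change | 0.3 | 8.3 | 66% | 47% | 11.8 | 222 |
| Change | 0.5 | 7.0 | 80% | 61% | 10.0 | 158 |
| Change | 0.7 | 5.4 | 95% | 83% | 7.7 | 96 |
| Adjusted score | 0.3 | 6.7 | 84% | 65% | 9.5 | 144 |
| Adjusted score | 0.5 | 6.1 | 90% | 74% | 8.7 | 120 |
| Adjusted score | 0.7 | 5.0 | 98% | 88% | 7.1 | 82 |

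Section 16 does not plan the adjusted analysis; it is shown because it is a natural candidate if a rule is written.

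**6. A caution only.** The plan does not say that p > 0.05 would be read as success. If it were, and digital were truly 5, 7 or 10 points worse on the unadjusted score, the two-sided test would be non-significant 71%, 50% or 20% of the time. The conclusion does not rest on this.

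**The case against.** The strongest reply is that one loosely phrased sentence carries the whole non-inferiority reading. Sections 9 and 16 fit each other as a difference trial, sections 5 and 7 claim nothing else, and rewording section 6 would cure the problem without changing the sample size, data or tests. On that view this is a drafting matter. It is true that the cure is cheap. But the sentence is the only hypothesis the trial states, and it determines what may be concluded when the arms are similar. Low cost does not make the mismatch minor.

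A second reply is that the 10-point important change is an implied margin, at which 102 gives 80% power. Section 9 presents it as a difference to detect. Accepting a deficit as large as the plan's own minimal important change would need an explicit justification, and none is given.

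A third is that the data will allow an interval anyway. They will; what is missing is a rule fixed beforehand.

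Some smaller points stand. The 12-week reference and the unranked analysis sets would be defects under a superiority hypothesis too, and they add nothing to the seriousness of this point. Section 8.1 reads most naturally as change from baseline, and section 9 makes it likely that section 16's 0.05 is two-sided. The power figures show what a margin might cost; they do not measure the defect.

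**Conclusion.** The concern holds and should be corrected before the analysis. The hypothesis in section 6 does not match the sample size in section 9 or the tests in section 16, and for similar arms the plan has no defined conclusion.

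That finding needs no assumption beyond the text, and neither does the 95% chance of a non-significant result on each planned test under equality. The half-width of about 7.0 points and the power of 29% to 80% across margins of 5 to 10 rest on 51 analysed per arm and an 8-week SD of 17.83. They move with the endpoint, correlation and dropout as tabulated. Whether 102 patients are enough for the hypothesis as worded cannot be judged until a margin and a primary quantity are named.

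**What to change.** Choose one of two before the analysis, and in either case reconcile section 16's 12-week time point with sections 8.1 and 15.

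**(a) Keep the hypothesis.**

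- Name one primary quantity: 8-week ODI score, change from baseline, or baseline-adjusted score.
- Pre-specify and justify an ODI margin.
- Conclude non-inferiority if the upper limit of the two-sided 95% confidence interval for digital minus conventional (higher is worse) lies below the margin. State whether the mean difference or the Hodges-Lehmann estimate carries that interval.
- State which of the intention-to-treat and per-protocol analyses decides, and the role of the other.
- Report the power that 102 gives for that margin and quantity, with the SD, correlation and dropout assumed.

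**(b) Restate section 6 as a superiority (difference) hypothesis** matching sections 9 and 16. Report the 95% confidence interval, and state that a non-significant result will not be presented as showing that digital is at least as good.

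**Cost.** Both options are wording only if 102 is kept. Under (a) the stated power may fall below 80%. More patients are needed only if the sponsor wants 80% power at a margin that 102 does not support: at an assumed margin of 8 on the unadjusted score, 158 in total before dropout, that is 158 − 102 = 56 more. Under (b) the cost is one or two sentences and a narrower claim, since a trial with similar arms would then not meet its hypothesis.

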## SH-RCT-LBP-US-01 Clinical Investigation Protocol

### 7. STUDY DESIGN

Prospective, single-center, parallel-group, randomised controlled study.

### 8. STUDY OUTCOMES

#### 8.1 Primary Outcome

Impact on functional disability measured through the Oswestry Disability Index score (patient reported outcome measure) between baseline and 8 weeks.

#### 8.2 Secondary Outcomes

The secondary outcomes will include the following, measured between baseline and 8 weeks:

